8.5.2.1.3 Subgroup Analysis

Subgroup analyses using the same methods as the primary and secondary analyses as described in sections 8.5.2.1 and 8.5.2.1.1 will be conducted comparing the primary efficacy endpoint between the treatment group and control group to assess consistency of treatment effects across potential prognostic factors.

The following subgroup of mITT will be analyzed for the primary efficacy endpoint.

- AIS grade (A, B vs C, D)
- Received study drug in Part 1 vs. Did not receive study drug in Part 1
- AIS grade (A vs. B, C, D)
- Time since injury ≤ 5 years vs >5 years

No adjustment to the significance level for testing will be made for subgroup analysis since all these subgroup analyses will be considered exploratory.

8.5.2.2 Secondary Efficacy Endpoints

- For Change from baseline in GRASSP Bilateral PP total score to Study Day 169, analysis will be conducted using the same methodology as that used for the primary efficacy endpoint (sections 8.5.2.1 and 8.5.2.1.1).
- For Change from baseline in SCIM III Self Care score to Study Day 169, analysis will be conducted using the same methodology as that used for the primary efficacy endpoint (sections 8.5.2.1 and 8.5.2.1.1).
- Fisher's exact test at two-sided significance level 0.05 will be used to test if there is a difference of PGIC responses (1=`Much worse', 2=`Worse', 3=` A little worse', 4=`No change', 5=`A little better', 6=`Better, 7=`'Much better') at Study Day 169 between patients in treatment group and control group. In addition, Fisher's exact test to compare responder rate (proportion of patient in mITT Analysis set with responses of `A little better', `Better', or `Much better') at Study Day 169 between the two treatment groups will conducted. A descriptive table summarizing number and percentage of patients for each of the seven above responses by visit and treatment group will be created.

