## 15.3. General Methods

Data will be tabulated using both descriptive and inferential statistics where specified.

- For Part 1, data will be tabulated by dosing cohort as well as pooled (all subjects combined), and no inferential statistics are planned.
- For Part 2, data will be tabulated for each treatment group separately (placebo and AXER-204) to allow for visual inspection of outcomes between the arms. Inferential comparison of the treatment groups is planned.

For both Parts, all data collected will be included in by-domain data listings, sorted by subject number and time point, or as appropriate.

No hypothesis testing will be performed for demographics, background, or safety data.

Continuous data will be summarized by presenting the number of subjects (n), means, mean changes from baseline, mean % changes from baseline (where appropriate), standard deviations, minimum, First quartile (Q1), median, third quartile (Q3), and maximum values. The number of subjects with missing data will be indicated.

Categorical data will be summarized by presenting the number of subjects (n), the number of subjects with missing data as well as counts and percentages in each of the categories. Percentages will be based upon the number of subjects with available data.

When inferential testing is applied to all efficacy assessments, dichotomous/binary categorical efficacy endpoints will be assessed via a 2-sided Fisher's Exact test or Chi-square test as appropriate. Continuous efficacy endpoints will also present least-squares means and p-values from hypothesis testing of efficacy endpoints using mixed-effects model for repeated measures (MMRM).

Additional details will be included in the statistical analysis plan (SAP) which will be finalized prior to unblinding Part 2 of the study and any amendments to it made prior to locking the database and unblinding the study.

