## 15.10. Efficacy Endpoints

For Part 1 efficacy, outcomes will be presented by each dosing cohort, with no inferential assessments among cohorts planned. Thus, for Part 1, efficacy will be presented only descriptively.

For Part 2, changes from pre-treatment to each on-treatment time point will be calculated, with the primary time point at Day 169. Shifts over time in ordinal endpoints will be presented, with comparisons between treatment groups assessed using a CMH row mean scores statistic at each time point. Slope of change will also be evaluated. Part 2 efficacy analysis is described in the following sections.

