3.1.2.4.5 Population-level Summary for Comparison between Treatment Conditions

The treatment effect will be the difference between AXER-204 and placebo in percentages of PGIC responder rate at Study Day 169 as estimated through a Fisher's Exact Test as defined in section 8.5.2.2.

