3.1.2.5.2 Other exploratory efficacy endpoints

- ISNCSCI ASIA impairment scale (AIS) with scales including A, B, C, D, E (protocol Appendix 3) at Study Day 169.
- ISNCSCI Neurological Motor level at Study Day 169.
- ISNCSCI Neurological Sensory level at Study Day 169.
- ISNCSCI Neurological Level of Injury (NLI) at Study Day 169.
- ISAFSCI assessments at Study Day 169. The ISAFSCI documents autonomic control of the heart, blood pressure, sweating and temperature regulation with findings equal to one of the following values: Normal, Abnormal, Unknown, or Unable to assess. Scores for lower urinary tract, bowel or sexual function will also be collected whereas score 0= complete loss of control; 1= Reduced or Altered Neurological Function; 2 = Normal function; NT=Unable to assess.
- Clinical Global Impression of Change (CGIC) from GRASSP Prehension Performance Video Recordings. Details are included below as this measure has been added beyond specific information included in the protocol. Conducted by a blinded rater who is trained on the scales and also has a C5/C6 injury to provide the perspective of the patient population we intend to treat with our therapy: Given the importance of this measure for functional, ADL as well as patient/clinically relevant changes, the GRASSP prehension performance assessment is video recorded at each time point to visually document changes reflected in the scoring as well as changes that may or may not be captured on the scale.

CGIC Evaluation

Compared to baseline, how would you describe the overall change (if any) related to performance of the GRASSP prehension performance tasks?

Choose ONE.

- ____Much worse (1)
- _____Worse (2)
- _____A little worse (3)
- ____No change (4)
- _____A little better (5)
- _____Better (6)
 - ___Much better (7)

If better or worse, what has changed? _

With the exception of the CGIC, all efficacy endpoints will also be analyzed for Study Day 253.

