8.5.2.3 Exploratory Efficacy Endpoints

For exploratory efficacy endpoints of changes from baseline in assessment results (as listed in section 3.1.2.5.1), analysis will be conducted using the same methodology as that used for the primary efficacy endpoint (sections $\underline{8.5.2.1}$ and $\underline{8.5.2.1.1}$).

For other exploratory efficacy endpoints at Study Day 169:

- ISNCSCI ASIA impairment scale (A, B, C, D, E) will be summarized descriptively as the number and percent of subjects with each response at each visit by treatment group.
- ISNCSCI Neurological Motor level will be summarized descriptively as the number and percent of subjects by body part by treatment group.
- ISNCSCI Neurological Sensory level will be summarized descriptively as the number and percent of subjects by body part by treatment group.
- ISNCSCI Neurological Level of Injury (NLI) will be summarized descriptively as the number and percent of subjects by body part by treatment group.
- ISAFSCI assessments: for each system/organ, shift table of baseline evaluation to Study Day 169 evaluation will be created.
- Clinical Global Impression of Change (CGIC) from GRASSP Prehension Performance Video Recordings. Assessments of Baseline compared to Day 169 will be completed and scores will be assigned using the 7-point Likert scale questions shown below and the Fisher's exact test at two-sided significance level 0.05 will be used to test if there is a difference in ratings (1= 'Much worse', 2='Worse', 3=' A little worse', 4='No change', 5='A little better', 6='Better, 7=''Much better') at Study Day 169 between patients in treatment group and control group. In addition, the Fisher's exact test will be used to compare responder rate (proportion of patient in mITT Analysis set with responses of 'A little better', 'Better', or 'Much better') at Study Day 169 between the two treatment groups. A descriptive table summarizing number and percentage of patients for each of the seven above responses by visit and treatment group will be created.

All efficacy endpoints will also be analyzed for Study Day 253 similar to the analysis conducted for Study Day 169 for each corresponding endpoint. All post treatment values up until Study Day 253 will be included in the analysis of treatment effect for Study Day 253.

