9.1 Secondary efficacy endpoint

Patient Global Impression of Change (PGIC) responder rate will be considered secondary efficacy endpoint.

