9.3 Analysis population

PK Analysis set and ADA analysis set were added in the SAP for analysis for PK and ADA, respectively. In addition, mITT analysis set was added for Part 2 and all Part 2 efficacy analysis will be conducted using mITT analysis set.

10. Changes in the Planned Statistical Analyses

The following changes in the planned statistical analyses indicated below are being made after all enrolled Part 2 patients have completed the 6-month visit, cleaning and unblinding of data, and completion of the 6-month top-line analysis for the primary, secondary and exploratory efficacy endpoints to compare treatment effects from baseline to Study Day 169 and prior to final database lock following 9-month visit or Study Day 253 (as described in section 2.2). The availability of results of this analysis was limited to the unblinded ReNetX staff and **Compare** Biostatistics and Programming team. The changes were requested by the unblinded ReNetX staff after review of results and approved by **Compare** Biostatistics and Programming team.

10.1 Post Hoc Exploratory Analysis for Efficacy Endpoints to Study Day 169

Results from the primary efficacy analysis, based upon a mixed-effects model for repeated measures (MMRM) as described in section 8.5.2.1, showed that there was no statistically significant difference at the two-sided 5% significance level between AXER-204 and Placebo groups in the primary efficacy endpoint. Additionally, the MMRM subgroup exploratory analyses (as described in section 8.5.2.1.3) did not show statistical significant difference between treatment and control groups in the primary endpoint at the unadjusted two-sided 5% significance level, but there is visually a potential trend toward treatment effect in the subgroups AIS grade (B, C, D) and no prior receipt of study drug in Part 1.

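### The SAP tests the seven ordered PGIC and CGIC categories with an order-blind Fisher's exact test, against the protocol's general rule for ordinal endpoints, and does not declare the change

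*SAP*

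**What the plan says.** **Protocol.** Section 15.3 says that "dichotomous/binary categorical efficacy endpoints will be assessed via a 2-sided" Fisher's exact or chi-square test. Section 15.10, on shifts over time in ordinal endpoints, has "comparisons between treatment groups assessed using a CMH row mean scores statistic at each time point". The synopsis repeats both rules.

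**SAP, seven-level tests.** Section 8.5.2.2 applies Fisher's "exact test at two-sided significance level 0.05 will be used to test if there is a difference of PGIC responses" at Day 169, across all seven categories from 1 (much worse) to 7 (much better). Section 8.5.2.3 uses the same scale for CGIC, where Fisher's "exact test at two-sided significance level 0.05 will be used to test if there is a difference in ratings".

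**SAP, responder tests.** Both sections add a separate Fisher test of the responder rate (categories 5 to 7). The PGIC estimand rests on that rate: section 3.1.2.4.5 defines the effect as the "difference between AXER-204 and placebo in percentages of PGIC responder rate at Study Day 169".

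**Declared changes.** SAP 9.1 says that "Patient Global Impression of Change (PGIC) responder rate will be considered secondary efficacy endpoint", and SAP 9.2 adds CGIC. Neither mentions the test. Section 10, on later changes to the planned analyses, does not mention it either.

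**The concern.** Fisher's exact test on a 2×7 table treats the categories as unordered labels. It asks whether the two distributions differ in any way, not whether one arm did better. A global impression of change is a question about direction.

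The seven-level PGIC test comes first under Secondary Efficacy Endpoints, at two-sided 0.05, with the responder test as an addition. Its p-value will therefore be reported and read as evidence on patient-perceived benefit. It could mislead in two ways: a significant result with no shift towards improvement, or a non-significant result when one arm is clearly shifted upwards. A reader who relies on Section 9 for the list of departures from the protocol would not know that the method for ordinal endpoints had been replaced.

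**Working it through.** The plan states no figure for these tests, so there is none to reproduce. The check has three parts.

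**1. Text.** The protocol sets one rule for ordinal endpoints (CMH row mean scores) and one for binary endpoints (Fisher or chi-square). PGIC and CGIC are ordered 1–7 scales. The SAP applies the binary method to all seven levels. The SAP's analysis sections contain no CMH test, and Sections 9 and 10 do not mention dropping it.

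**2. Two worked tables.** The counts are invented, for categories 1 to 7, with 16 per arm (from about 32 randomised 1:1). The CMH row mean scores statistic with scores 1–7, unstratified, is (N − 1)r² on 1 df, where r² is the between-arm share of the total sum of squares of the scores. Fisher p-values are by full enumeration.

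*Table A: (0,4,1,6,1,4,0) vs (0,0,5,6,5,0,0).*
- The score sums are 64 and 64, so both means are 64/16 = 4.0. Responders are 5/16 in both arms.
- r² = 0, so the CMH statistic is 0 and p = 1.0. Responder Fisher p = 1.0.
- Seven-level Fisher p = 0.007.

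*Table B: (0,0,1,4,5,4,2) vs (0,1,3,7,4,1,0).*
- The score sums are 82 and 65, so the means are 5.125 and 4.0625.
- Total sum of squares: 719 − 147²/32 = 43.72. Between arms: 32 × 0.53125² = 9.03.
- r² = 9.03/43.72 = 0.2066. The statistic is 31 × 0.2066 = 6.40, so CMH p = 0.011 (permutation p = 0.014).
- Responders are 11 vs 5, Fisher p = 0.076.
- Seven-level Fisher p = 0.30.

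Table A is significant with no shift. Table B is a shift of about one category that the seven-level test misses.

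**3. Power, under assumed distributions.** Placebo percentages from much worse to much better are (1,4,10,50,22,10,3), with 35% responders, and (1,3,6,65,17,6,2), with 25% responders. The active arm is a proportional-odds shift. There are 16 per arm, two-sided 0.05, and 3,000 simulated trials per setting.

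| Odds ratio | Fisher vs CMH, 35% responders | Fisher vs CMH, 25% responders |
|---|---|---|
| 2 | 10% vs 18% | 8% vs 15% |
| 3 | 19% vs 35% | 18% vs 30% |
| 4 | 31% vs 53% | 29% vs 47% |
| 6 | 47% vs 75% | 49% vs 69% |
| 8 | 63% vs 86% | 62% vs 82% |

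The CMH figures use the asymptotic p-value. With a permutation p-value the gain over Fisher is 0–5 points at odds ratio 2 and 12–17 at odds ratio 4. Size at odds ratio 1 is 4.3–5.3% for seven-level Fisher, 4.7–5.0% for CMH and 3.0–3.6% for permutation CMH.

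Other shapes of difference:
- **One-step benefit only** (no change to a little better). With 30 points moved, Fisher has 42% and CMH 13–16%. With 40 points moved, 64–70% and 20–25%. The ranking reverses.
- **Larger benefit** (35 points moved to better or much better). Fisher 53% vs CMH 46% under one placebo distribution and 51% vs 54% under the other, so the two are similar.
- **Spread only**: (0,5,20,50,20,5,0)% vs (10,10,5,50,5,10,10)%, both with mean 4.0 and 25% responders. Seven-level Fisher rejects 40% of the time, CMH 4.5% and the responder test 2% (2,000 trials).

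**The case against.** **The protocol rule may not cover PGIC.** The CMH sentence opens with shifts over time in ordinal endpoints and does not name PGIC, which is already a rating of change. Protocol 15.10.1 lists PGIC among changes from baseline, and 15.3 leaves further detail to the SAP. CGIC is a declared SAP addition with no protocol method of its own. This stands as a limit: the departure is from a general rule for ordinal endpoints, not from an analysis assigned to PGIC by name. That sentence is still the only between-group test the protocol gives for ordinal endpoints, and a 1–7 worse-to-better scale is ordinal by its form.

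**No named endpoint depends on this test.** The PGIC estimand and both of its sensitivity analyses use the responder rate, and all seven categories will be tabulated by arm, so direction will be visible. This also stands, and it limits the consequence. The seven-level p-values will nevertheless be reported at 0.05.

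**Fisher is valid and sometimes more powerful.** Its type I error is correct, and Table A does show a real difference in distribution. If benefit is a single-step move, Fisher wins clearly. That case is plausible, because the SAP counts a little better as response and says that small changes may matter in chronic injury. Neither test is best for every shape of benefit. The case for CMH is that it addresses direction and is the protocol's method.

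**Changing the test after unblinding is data-dependent.** SAP Section 10 records changes that "are being made after all enrolled Part 2 patients have completed the 6-month visit, cleaning and unblinding of data". This stands, so a CMH result can only be an addition to the planned Fisher result and must be labelled as such.

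**Conclusion.** The concern holds. The SAP replaces the protocol's method for ordinal endpoints with an order-blind test for the seven-level PGIC and CGIC comparisons, and does not say so. That the test ignores order does not depend on any assumption; Tables A and B show both ways it can mislead.

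The size does depend on assumptions, because the documents give no PGIC distribution. For a proportional-odds shift at 16 per arm, asymptotic CMH gains 12–28 points of power at odds ratios 3 to 8, and less with a permutation p-value. For a one-step benefit it loses power. The stratified form was not simulated.

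The scope is limited. The UEMS analysis and the PGIC responder rate are untouched. The point is worth correcting because the departure is undeclared, bears on a patient-reported measure and is cheap to put right.

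**What to change.** - In SAP 8.5.2.2 and 8.5.2.3, name the CMH row mean scores test (scores 1–7, exact or permutation p-value, stratified by the randomisation factors where cell sizes allow) as the seven-level comparison for PGIC and CGIC. Leave the responder-rate Fisher tests as they are.
- List any departure from protocol 15.10 in SAP Section 9, with the reason. If the sponsor prefers to keep seven-level Fisher, this entry is the minimum.
- At Day 169, report the CMH result beside the planned Fisher result, labelled as added after unblinding to restore the protocol's method.
- At Day 253, fix the CMH test for PGIC before the final database lock, with the same label. SAP 3.1.2.5.2 leaves CGIC out at that visit: "With the exception of the CGIC, all efficacy endpoints will also be analyzed for Study Day 253".

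The cost is SAP wording, one procedure option and one labelled extra result, with no new data. There are four drawbacks. Category scores must be assigned. Power is lower than seven-level Fisher if benefit is a one-step move only. The permutation p-value costs about 3–8 points of power against the asymptotic CMH. The Day 169 CMH result cannot be presented as pre-specified in the SAP.

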8.5.2.2.1 Sensitivity Analysis

- For Change from baseline in GRASSP Bilateral PP total score to Study Day 169 and Change from baseline in SCIM III Self Care score to Study Day 169, sensitivity analyses will be conducted using the same methodology and model as that used for the primary efficacy endpoint (section 8.5.2.1.2).
- For PGIC responder rate, the analysis described above will be conducted for the per protocol set to evaluate if deviations from protocol affect treatment effect assessed by PGIC.
- For PGIC responder rate, the analysis described above will be repeated, except subjects who discontinued the study prior to the assessment scheduled for Study Day 169 will be assigned a response of 4='No change'. This analysis will use the composite variable strategy, to assess the sensitivity of the results to the occurrence of the intercurrent events like discontinuation from the study prior to assessment scheduled on Study Day 169 as described in section 3.1.2.4.6.

8.5.2.3 Exploratory Efficacy Endpoints

For exploratory efficacy endpoints of changes from baseline in assessment results (as listed in section 3.1.2.5.1), analysis will be conducted using the same methodology as that used for the primary efficacy endpoint (sections $\underline{8.5.2.1}$ and $\underline{8.5.2.1.1}$).

For other exploratory efficacy endpoints at Study Day 169:

- ISNCSCI ASIA impairment scale (A, B, C, D, E) will be summarized descriptively as the number and percent of subjects with each response at each visit by treatment group.
- ISNCSCI Neurological Motor level will be summarized descriptively as the number and percent of subjects by body part by treatment group.
- ISNCSCI Neurological Sensory level will be summarized descriptively as the number and percent of subjects by body part by treatment group.
- ISNCSCI Neurological Level of Injury (NLI) will be summarized descriptively as the number and percent of subjects by body part by treatment group.
- ISAFSCI assessments: for each system/organ, shift table of baseline evaluation to Study Day 169 evaluation will be created.
- Clinical Global Impression of Change (CGIC) from GRASSP Prehension Performance Video Recordings. Assessments of Baseline compared to Day 169 will be completed and scores will be assigned using the 7-point Likert scale questions shown below and the Fisher's exact test at two-sided significance level 0.05 will be used to test if there is a difference in ratings (1= 'Much worse', 2='Worse', 3=' A little worse', 4='No change', 5='A little better', 6='Better, 7=''Much better') at Study Day 169 between patients in treatment group and control group. In addition, the Fisher's exact test will be used to compare responder rate (proportion of patient in mITT Analysis set with responses of 'A little better', 'Better', or 'Much better') at Study Day 169 between the two treatment groups. A descriptive table summarizing number and percentage of patients for each of the seven above responses by visit and treatment group will be created.

All efficacy endpoints will also be analyzed for Study Day 253 similar to the analysis conducted for Study Day 169 for each corresponding endpoint. All post treatment values up until Study Day 253 will be included in the analysis of treatment effect for Study Day 253.

8.6 Pharmacokinetic Assessment

8.6.1 Pharmacokinetic Analysis

In Parts 1 and 2, individual serum and CSF concentrations at each sampling timepoint for AXER-204 will be presented by listings and descriptive summary statistics. Individual and mean serum and CSF concentration versus time data will be plotted

on linear and semi-logarithmic scales. In Part 1, all PK parameters will be presented by individual listings and summary statistics.

Summary statistics for concentration and PK parameter data will include the arithmetic mean, arithmetic standard deviation, median, minimum, maximum, number of observations, geometric mean and geometric coefficient of variation (CV%).

In Part 1, the following pharmacokinetic parameters will be determined where possible from the serum and CSF concentrations of AXER-204 using non-compartmental methods performed using Phoenix WinNonlin (Certara, Inc., Version 8.1 or higher):

Parameter	Definition
$AUC_{0-tlast}$	Area under the concentration-time curve from time zero to the time
	of the last quantifiable concentration
$AUC_{0-\infty}$	Area under the concentration-time curve from time zero to infinity
%AUC _{extrap}	Area under the concentration-time curve extrapolated from last
	quantifiable concentration to infinity as a percentage of total AUC
C _{max}	Maximum observed concentration
t _{max}	Time of the maximum observed concentration
t _{1/2}	Apparent terminal elimination half-life
CL/F	Apparent total serum clearance
V _z /F	Apparent volume of distribution during the terminal elimination
	phase (serum only)

In addition, dose normalised values (suffixed DN) for $AUC_{0-tlast}$, $AUC_{0-\infty}$ and C_{max} will be determined by dividing the original PK parameter by mg.

Additional pharmacokinetic parameters may be determined where appropriate.

Pharmacokinetic analysis will, where possible, be carried out using actual post-dose times recorded in the raw data. If actual sampling times are missing, nominal times may be used.

Concentrations are used as supplied by the analytical laboratory for PK analysis. The units of concentration and resulting PK parameters, with amount or concentration in the unit, will be presented as they are received from the analytical laboratory.

 C_{max} and t_{max} will be obtained directly from the plasma concentration-time profiles.

CONFIDENTIAL

For multiple peaks, the highest postdose concentration will be reported as C_{max} . In the case that multiple peaks are of equal magnitude, the earliest T_{max} will be reported.

AUC will be calculated using the linear trapezoidal method when concentrations are increasing and the logarithmic trapezoidal method when concentrations are decreasing (linear up/log down rule).

The parameters based on observed C_{last} will be reported.

The following regression related pharmacokinetic parameters will be determined and presented in the listings:

Parameter	Definition
λz	Elimination rate constant
λz upper	End of exponential fit
λz lower	Start of exponential fit
λz N	Number of data points included in the log-linear
	regression
t1/2_interval	Ratio of $t_{1/2}$ relative to the λz interval (λz upper - λz
ratio	lower)
Rsq_adj	Adjusted coefficient for determination of exponential fit

8.6.1.1 Criteria for Handling Concentrations Below the Limit of Quantification in Pharmacokinetic Analysis

- Concentration values that are below the level of quantification (BLQ) will be set to zero, with defined exceptions as follows;
 - Any embedded BLQ value (between 2 quantifiable concentrations) and BLQ values following the last quantifiable concentration in a profile will be set to missing for the purposes of PK analysis.
 - If there are late positive concentration values following 2 BLQ concentration values in the apparent terminal phase, these values will be evaluated. If these values are considered to be anomalous, they will be set to missing.
 - If an entire concentration-time profile is BLQ, the profile will be excluded from the PK analysis.

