8.6.1.2 Criteria for the Calculation of an Apparent Terminal Elimination Half-Life

• Number of Data Points

 $_{\odot}$ At least three data points will be included in the regression analysis and preferably should not include C_{max}.

• Goodness of Fit

- When assessing terminal elimination phases, the R² adjusted (Rsq_adj) value will be used as a measure of the goodness of fit of the data points to the determined line.
- An elimination half-life will generally only be calculated if the R² adjusted value of the regression line is greater than or equal to 0.7. Exceptions can be made (e.g. CSF) for exploratory purposes.

• Period of Estimation

- $\circ~$ Time period used for the estimation of apparent terminal elimination half-lives, where possible, will be over at least two half-lives (t_{1/2}_interval ratio).
- $\circ~$ Where t_{1/2}_interval ratio < 2 the robustness of the value(s) may be discussed in the study report.

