8.6.1.3 Calculation of AUC

- The minimum requirement for the calculation of AUC will be the inclusion of at least three consecutive concentrations above the lower limit of quantification (LLOQ), with at least one of these concentrations following C_{max} .
- For any partial AUC determination (i.e. AUC over a dosing interval), nominal time will generally be used for the end of the interval. Actual times for partial AUC intervals may be used at the discretion of the Pharmacokineticist.
- AUC_{0- ∞} values where the percentage extrapolation is less than 20% will be reported. AUC_{0- ∞} values where the percentage extrapolation is greater than 20% may be excluded from descriptive statistics at the discretion of pharmacokineticist.

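### Part 1 CSF AUC: as written, the SAP fills the unsampled first 24 hours with a straight rise from zero, giving at most about half the true area of that interval for any CSF curve that does not rise after injection

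*SAP*

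**What the plan says.** **Sampling and dosing.** Protocol 13.2 and Table 10 schedule Part 1 CSF before the dose, at 24 h (±2 h), at 72 h (±4 h), on Day 8 and on Day 29. Serum is also taken at 1, 6 and 12 h; CSF is not. Protocol 5.4 and 7.3.1 set the intrathecal injection rate at 100 mL/h, 12 minutes for 20 mL.

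**Parameters.** SAP 8.6.1 lists AUC0-tlast, AUC0-∞ and Cmax among the quantities that "will be determined where possible from the serum and CSF concentrations of AXER-204 using non-compartmental methods". Dose-normalised versions of these three "will be determined by dividing the original PK parameter by mg".

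**Calculation rules.** The same rules serve both fluids. For area: "AUC will be calculated using the linear trapezoidal method when concentrations are increasing and the logarithmic trapezoidal method when concentrations are decreasing". For low values, section 8.6.1.1 says: "Concentration values that are below the level of quantification (BLQ) will be set to zero". Its exceptions cover values lying between two quantifiable ones, values after the last quantifiable one, late anomalous positives and profiles with no quantifiable value. None covers a pre-dose value.

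**Half-life and AUC criteria.** For the terminal slope, section 8.6.1.2 says: "At least three data points will be included in the regression analysis and preferably should not include" Cmax. Its one mention of CSF, "Exceptions can be made (e.g. CSF) for exploratory purposes", relaxes the R² threshold for half-life. Section 8.6.1.3 requires "at least three consecutive concentrations above the lower limit of quantification (LLOQ), with at least one of these concentrations following" Cmax. It also provides that AUC0-∞ "values where the percentage extrapolation is greater than 20% may be excluded from descriptive statistics".

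The SAP has no back-extrapolated starting concentration and no separate rule for the first CSF interval.

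**The concern.** A line rising from zero to the first sample suits a drug that is absorbed slowly into the sampled fluid. Here the drug is placed in that fluid within minutes, by lumbar puncture, and the fluid is later sampled by lumbar puncture. The concentration is likely to be at or near its highest shortly after injection, when the calculation puts it near zero.

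Pharmacokinetics is part of the Part 1 primary objective, and CSF is the compartment dosed. A table of CSF AUC from time zero would carry a first interval that was never sampled and was filled by an unsuitable rule, with nothing to warn the reader. The dose-normalised AUCs would inherit it.

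**Working it through.** **Inputs from the documents.** Injection: 20 mL / 100 mL/h = 0.2 h = 12 min, as the protocol states. CSF times: 0, 24, 72, 168 (Day 8) and 672 h (Day 29). Pre-dose value: zero, because Part 1 is the first human exposure (Protocol 5.3) and no exception in SAP 8.6.1.1 applies. The documents give no CSF half-life and no limit of quantification, so half-lives below are assumptions shown over a range.

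**1. The first segment.** Linear trapezoid from (0, 0) to (24, C24): 0.5 x 24 x C24 = 12 x C24. With actual times over 22-26 h the factor is 11 to 13.

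**2. Bound on that segment.** If the curve does not rise after 0.2 h, the true area to time ts is at least (ts - 0.2) x C(ts). The captured share is therefore at most:
- 22 h: 11/21.8 = 50.5%
- 24 h: 12/23.8 = 50.4%
- 26 h: 13/25.8 = 50.4%

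No half-life is assumed.

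**3. Reported AUCs, mono-exponential decline.** Let k = ln2/t½. The log rule is then exact after 24 h, so

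AUC0-∞ ratio (SAP/true) = exp(-24k)(1 + 12k)

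AUC0-tlast ratio = [12·C24 + (C24 - Ctlast)/k] / [C0(1 - exp(-k·tlast))/k]

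| Assumed t½ | AUC0-∞ | AUC0-tlast, Day 8 | AUC0-tlast, Day 29 |
|---|---|---|---|
| 24 h | 0.67 | 0.67 | not expected |
| 48 h | 0.83 | 0.81 | 0.83 |
| 96 h | 0.91 | 0.88 | 0.91 |
| 168 h | 0.95 | 0.90 | 0.95 |

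The AUC0-∞ loss drops below 10% above a half-life of about 83 h and below 5% above about 166 h.

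The 24 h row needs care. With C0 = dose/150 mL (the CSF volume named in Protocol 5.4), 3 mg gives 20,000 ng/mL. Day 29 is 28 half-lives later: 20,000/2^28 = 0.00007 ng/mL (0.005 ng/mL for 200 mg), unlikely to be quantifiable. The terminal slope would then need C24, which the SAP prefers to leave out because it is the observed Cmax. At 48 h, Day 29 is 20,000/2^14 = 1.2 ng/mL (81 ng/mL for 200 mg).

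**4. Reported AUCs, slow bi-exponential decline.** The log trapezoid over Day 8 to Day 29 (504 h) overstates a curve that flattens. Example: C(t) = 0.9·2^(-t/72) + 0.1·2^(-t/500), instantaneous input.

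| Interval (h) | SAP area | True area | Difference |
|---|---|---|---|
| 0-24 | 9.73 | 21.65 | -11.91 |
| 24-72 | 32.00 | 31.95 | +0.05 |
| 72-168 | 36.66 | 36.33 | +0.33 |
| 168-672 | 59.32 | 47.14 | +12.18 |
| Total | 137.71 | 137.06 | +0.65 |

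The total is right to 0.5%, although two of its four pieces are badly wrong. The same calculation on four such curves, as SAP/true:

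| Half-lives, slow fraction | AUC0-tlast, Day 29 | AUC0-tlast, Day 8 | AUC 24 h-Day 29 | AUC 24 h-Day 8 |
|---|---|---|---|---|
| 72 and 500 h, 10% | 1.005 | 0.87 | 1.109 | 1.006 |
| 72 and 720 h, 5% | 1.002 | 0.87 | 1.119 | 1.004 |
| 96 and 720 h, 10% | 1.007 | 0.89 | 1.087 | 1.003 |
| 48 and 500 h, 5% | 0.967 | 0.83 | 1.132 | 1.011 |

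**5. Cohort comparisons.** Under linear kinetics with a common last sampling time, the proportional error is the same in every cohort. If one cohort's last quantifiable sample is Day 29 and another's is Day 8, the mono-exponential AUC0-tlast ratio shifts by a factor of 1.020, 1.041 or 1.051 at 48, 96 or 168 h.

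**The case against.** The strongest objection is to the direction of the error. A reader might infer that both CSF AUCs are always too low. The documents do not support that. Step 4 shows strictly declining curves for which AUC0-tlast to Day 29 is correct or very slightly high. Protocol 5.2 reports that tissue half-life outlasted CSF half-life in animals, so a multiphasic CSF curve is plausible. This objection stands: only the 0-24 h segment is low for every non-rising curve.

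Second, replacing the measure has its own weakness. On the same four curves, AUC from 24 h to Day 29 is 9-13% high. This also stands, and the fix allows for it.

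Third, the consequences are limited. The protocol's PK endpoint is a description of concentrations over time. Individual CSF concentrations are listed and plotted, Part 1 has no inferential analysis, and Protocol 7.3.3.1 does not require PK results for escalation unless they are judged advisable. This keeps the point modest but does not make the tabulated segment right.

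Fourth, the SAP leaves some room: parameters are derived only where possible, partial AUCs and additional parameters are allowed, and sampling times may change for later cohorts. None of this corrects the calculation. Samples at 24 h, 72 h and Day 8, if quantifiable, meet the three-value minimum. No earlier CSF time is specified, although the 24 h gap is certain only for the first cohort. The 20% extrapolation clause deals with the tail, not the start.

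**Conclusion.** The point holds for the first segment. Followed as written, the SAP computes the 0-24 h part of CSF AUC0-tlast and AUC0-∞ as 12 x C24. That is at most about half of its true area, provided the CSF concentration does not rise after injection and the pre-dose value is below quantification.

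The net error in the reported AUCs cannot be fixed from the documents. It ranges from a loss of about a third (24 h half-life, with the conditions given above) through 5-19% at half-lives of 48-168 h, to almost none where the Day 8-29 interval happens to compensate. Agreement reached by cancelling errors is no support for the method.

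A reader might also infer that dose escalation or the Part 2 regimen rests on distorted CSF exposure. The documents do not show this. Serum parameters, λz and half-life do not use the 0-24 h CSF segment, and the non-compartmental analysis is confined to Part 1. Cohort ratios under linear kinetics move by only about 2-5% in the cases examined. This is a reporting defect in descriptive CSF exposure tables that is worth correcting because the correction is simple.

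**What to change.** Add a CSF rule to SAP 8.6.1:
- A pre-dose zero is not used as the time-zero concentration for CSF AUC.
- Report C24 and AUC from 24 h to the last quantifiable sample as the CSF exposure measures over the sampled range. Report AUC from 24 h to Day 8 as well, with a note that the log rule over the long Day 8-29 interval can overstate a multiphasic curve.
- Give CSF AUC from time zero only with a back-extrapolated starting concentration, labelled model-dependent.
- Footnote CSF Cmax and tmax as limited by the time of the first post-dose sample.

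The serum, λz and half-life rules stay as they are. The reference to plasma profiles in 8.6.1 should read serum and CSF; that is editorial and carries no weight here.

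The cost is SAP wording and a rerun of the CSF analysis on existing data, with no new samples. SAP 2.3.2 already cites Part 1 data, so the change should be logged as made after Part 1, and any existing CSF tables reissued. The downside is that CSF AUC0-∞ is no longer reported as an observed quantity.
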